4.2. Primary Endpoint

To compare the detection of arrhythmias between the two methods mentioned with regard to the set of the following arrhythmias: a) atrial fibrillation or atrial flutter; b) supraventricular tachycardia (≥ 3 beats); c) ventricular tachycardia (≥ 3 beats); d) polymorphic ventricular tachycardia or ventricular fibrillation; e) atrioventricular block (2nd degree Mobitz AVB I and II, 2:1 AVB and total AVB); and f) pauses (≥ 2.5 seconds). The comparison between the two methods will be evaluated by the accuracy of *QuoreOne* compared to the conventional system, in addition to the other diagnostic statistics: sensitivity, specificity, positive and negative predictive values will also be presented always followed by 95% confidence intervals.

4.3. Secondary Endpoints

Comparison of the detection of each type of arrhythmia between the two devices

- Comparison of the duration of the examination between the two devices;
- Comparison of mean, minimum, and maximum heart rate captured between the two devices;
- Comparison of the total atrial ectopic heart beats captured between the two devices;
- Comparison of total ventricular ectopic heart beats captured between the two devices;
- Comparison of total episodes of supraventricular tachycardia, ventricular tachycardia, and pauses between the two devices;
- Evaluate the convenience of using the two registration systems.

The individual categorical secondary endpoints (detection of each type of arrhythmia) will also be evaluated by diagnostic statistics (accuracy, sensitivity, specificity, positive and negative predictive values) with respective 95% confidence intervals.

The continuous secondary endpoints (mean, minimum and maximum heart rate, total atrial and ventricular ectopic heart beats, total episodes of supraventricular tachycardia, ventricular tachycardia and pauses) will be described by Bland-Altman plots accompanied by Lin and Pearson correlation coefficients.

Lists with the patient's reports will be made to evaluate the convenience of the systems. The Chi-square test or Fisher's exact test will be used to evaluate the

proportion of patients who report greater comfort (comfort of the device) with *Quoreone* versus *Cardiolight*.

4.4. Sample size calculation

The sample size calculation of the study was established assuming the hypothesis of comparability of the *QuoreOne* device in relation to the conventional device. Considering data from a previous study,⁷ a two-tailed alpha of 5% and a power of 80% for the primary endpoint, the study will need to include a minimum of 182 patients with valid and complete measures of the 24-hour records by both methods.

5. Ethical Aspects

## 1. INTRODUCTION

### 1.1. Rationale and Background

The 24-hour ambulatory electrocardiogram, performed by the Holder system, is a procedure whose objective is to find the correlation between symptoms and possible changes in the electrocardiogram in order to establish a cause-effect relationship. In practice, a digital recorder is connected to a cable with electrodes at its ends, which are then applied to the thoracic surface. The objective is for the electrical signal emitted by the heart to be captured and recorded in at least three channels that correspond to the electrocardiographic leads. Once captured, the signals recorded on a digital card are transferred to a computer that, by means of specific software, performs the analysis and issues a result that includes the maximum, minimum and mean heart rates, in addition to the total number of atrial and ventricular ectopic heart beats, total tachycardias and ST segment alterations and T waves. The interpretation of the electrocardiographic recordings is then carried out by a specialized technical analyst who confirms the data or corrects the information that is in disagreement. The following result is confirmed by a physician.

Current systems are limited to this type of analysis, but they suffer from some limitations. These are of a technical nature related to signal capture, the dependence on electrode cables, which often limit the mobility of patients and is associated with greater risks of interference in the recording channels (50/60 Hz electrical network, touching of clothing on the electrodes; electrode displacements, etc.). Depending on the intensity and duration of these alterations, there may be a need to repeat the examination.

With the advancement of technology, new signal capture systems have been developed. The possibility of applying the recorder directly to the thoracic surface eliminated the need for electrode cables. This fact not only improved the quality of the signs, but also allowed greater patient mobility, making the test better tolerated. The possibility of sending the recorded signals over the internet speeds up their interpretation. In addition, an analysis software previously trained by neural networks allows the editing of records more quickly by issuing a pre-report, facilitating the routine of the physician who will have less work to prepare the final report. With this approach, it is expected that the more exams the system analyzes, the better its performance should be, probably reaching almost the point of minimal medical interference in the final result.

In the study, which is now proposed to be carried out at the Cardiac Arrhythmias Outpatient Clinic of the Dante Pazzanese Institute of Cardiology (IDPC), Holter recordings will be performed in about 180 consecutive patients with the two systems simultaneously, the *QuoreOne* from Quoretech (system under test) and the *Cardiolight* from Cardios (conventional 24-hour Holter-system), a system that has been on the market for more than 30 years and is widely used in the country today. This approach will allow for the comparison of *QuoreOne*'s results with those of *Cardiolight*.

## 1.2. Objectives

### *Primary Objective:*

To assess whether the detection of arrhythmias by *QuoreOne* is comparable to *Cardiolight*. Detection of the following arrhythmias will be compared: atrial fibrillation or atrial flutter, supraventricular tachycardia, ventricular tachycardia, polymorphic ventricular tachycardia or ventricular fibrillation; atrioventricular block and pauses.

*Secondary Objective:* Compare the 24-hour electrocardiographic recordings detected by both systems. The following will be included in the analysis: a) maximum, minimum and mean heart rates; b) total atrial and ventricular ectopic heart beats; c) episodes of supraventricular tachycardia, ventricular tachycardia, and pauses. In addition to these variables, the duration of the examination and the convenience of using both systems should also be compared.

## 2. STUDY METHODS

### 2.1. Study Design

This is a comparative, single-center study with consecutive inclusion of patients. Research participants will be included prospectively.

All exams will be performed at IDPC, the exams performed with the *Cardiolight* equipment will be stored both in the original file (.xcm) and in the final version of the report (.pdf). The exams performed with the *QuoreOne* equipment will be saved directly on the online report platform and in the final version of the report (.pdf). These files will be exported to an external hard drive and sent for tabbing. The parameters will be analyzed with anonymized data from the participants.

After the Holter devices are removed, the participant will be asked to answer a questionnaire about the convenience of use and functions of the *QuoreOne* device.

The Holter-type cardiac monitor is a portable ambulatory electrocardiography device. It aims to monitor the electrical activity of the heart over a prolonged period, usually twenty-four hours.

For this study, the *Cardiolight* recorder from the company Cardios, the predominant equipment in the medical practice of the IDPC, and the *QuoreOne* recorder, from Quoretech, will be used, which will be submitted to comparison.

The exams performed by the conventional system (*Cardiolight*, Cardios) will be analyzed and the reports released by physicians from the Electrophysiology Section of the IDPC. These tests will be implemented at the same time in the same patient and for the same duration. The physicians evaluating the results of one method will be the same as the physicians evaluating the results obtained by the other method, but these will be blinded to the patients' data, making it impossible to identify that the tests being evaluated are from the same patient.

## 2.2. Randomization

This is a comparative, single-center study, where all patients included consecutively and prospectively, will use both systems simultaneously, Quoretech's *QuoreOne* and Cardios' *Cardiolight*. In this way, it will not be necessary to use any randomization technique.

## 2.3. Sample Size

The sample size calculation of the study was established assuming the hypothesis of comparability of the *QuoreOne* device in relation to the conventional device. According to data from a previous study, we have:

		Holter Any 6 (24 h)		Total
		No	At least 1	
Patch any 6 (24 h)	No	83	11	94
	Yes	2	50	52
Total		85	61	146

Any arrhythmias (of the 6 types atrioventricular block, pause, polymorphic ventricular tachycardia, supraventricular tachycardia, ventricular tachycardia, or atrial fibrillation)

From the data in the table above, we obtain the following proportions:

		Holter Any 6 (24 h)		Total
		No	At least 1	
Patch any 6 (24 h)	No	0.5685	0.0753	0.6438
	Yes	0.0137	0.3425	0.3562
Total		0,5822	0.4178	1.0000

Assuming that *QuoreOne* and Holter will agree to detect at least one arrhythmia event similar to that found between Patch and Holter in the reference study, a sample of 182 patients will have 80% power to show that the overall accuracy is greater than 85%, at a one-tailed significance level of 2.5%. (i.e., the lower limit of the 95% confidence interval (CI) should be above 85%). Therefore, this premise considers Holter as the "gold standard" test, and the accuracy of the *Quoreone* is evaluated in the detection of global arrhythmias (primary endpoint) and specific categories (secondary endpoints).

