2.1. Sample

It will consist of data from Holter recordings to be performed on patients from the Electrophysiology and Cardiac Arrhythmias outpatient clinic of the Medical Section of Electrophysiology of IDPC. The sample size calculation foresees the inclusion of a minimum of 182 patients with complete data from both exams.

2.2.Inclusion Criteria

 Patients aged ≥ 18 years, with indication for continuous 24-hour electrocardiographic monitoring by 24-hour Holter at the IDPC outpatient clinic, and who agree to participate in the study by signing the free and informed consent form (ICF).

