### 3. STATISTICAL PRINCIPLES

#### 3.1. Confidence Intervals and p-Values

Two-tailed hypothesis tests with a significance level of 5% and confidence intervals of 95% will be used.

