#### 4.3. Recruitment

All patients over 18 years of age who undergo Holter monitoring tests at the Electrophysiology and Cardiac Arrhythmias outpatient clinic of the Medical Section of Electrophysiology of the IDPC will be invited to participate in the study, and a prospective and consecutive recruitment of at least 182 patients with complete data from the two tests is expected.

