### Primary Endpoint

The comparison between the two methods in relation to the detection of arrhythmias will be evaluated by the accuracy of *QuoreOne* compared to Holter. The primary endpoint consists of the detection of any arrhythmia: a) atrial fibrillation or atrial flutter; b) supraventricular tachycardia ( $\geq 3$  beats); c) ventricular tachycardia ( $\geq 3$  beats); d) polymorphic ventricular tachycardia or ventricular fibrillation; e) atrioventricular block (2nd degree Mobitz AVB I and II, 2:1 AVB and total AVB); and f) pauses ( $\geq 2.5$  seconds). Other diagnostic statistics: Sensitivity, specificity, positive and negative predictive values will also be presented always followed by 95% confidence intervals.

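### At 182 patients no 95% interval delivers both the stated 80% power and the stated one-tailed 2.5% error, and the interval that decides the primary endpoint is not named

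*SAP*

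**What the plan says.** SAP 2.3 plans the study on the agreement table of a reference study and assumes that QuoreOne and Holter "will agree to detect at least one arrhythmia event similar to that found between Patch and Holter in the reference study". From this it concludes that "182 patients will have 80% power to show that the overall accuracy is greater than 85%, at a one-tailed significance level of 2.5" per cent. It then explains that level in terms of an interval: "the lower limit of the 95% confidence interval (CI) should be above 85" per cent. This is the only success criterion given for the primary endpoint.

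Protocol 4.4 repeats the size and power ("a power of 80% for the primary endpoint, the study will need to include a minimum of 182 patients") with a two-tailed alpha of 5%. That agrees with 2.5% per tail.

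No section names the type of interval:
- SAP 3.1 says only "Two-tailed hypothesis tests with a significance level of 5% and confidence intervals of 95% will be used".
- SAP 5.2, under the primary endpoint, says of the diagnostic statistics that they "will also be presented always followed by 95% confidence intervals".
- Protocol 4.2 gives the 95% level only.
- SAP 5.6 names the software but no method.

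The number 182 is a minimum count of complete pairs. Protocol 2.1 says "The sample size calculation foresees the inclusion of a minimum of 182 patients with complete data from both exams", and SAP 4.3 says "a prospective and consecutive recruitment of at least 182 patients with complete data from the two tests is expected".

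**The concern.** Common 95% intervals for a proportion differ noticeably at about 90% with fewer than 200 observations, and the margin here is narrow (91.1% against 85%). A rule that refers only to the lower 95% limit is therefore not one rule. Two things are at stake.

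First, the stated power and error may not both be true of any rule the SAP allows. Readers would then credit the primary analysis with properties it lacks.

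Second, if the interval is chosen after the data are seen, a borderline result can be made to pass or fail by that choice. The documents give no sign that anyone intends this. But the device's manufacturer funds the study, and an open choice on the only success criterion invites challenge.

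**Working it through.** **Inputs (SAP 2.3).** Null accuracy p0 = 0.85. Planning accuracy p1 = (83 + 50)/146 = 133/146 = 0.9110. n = 182 complete pairs. One-tailed level 2.5%, power 80%.

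**Method.** For each interval, find the smallest number of agreements r out of 182 whose lower 95% limit exceeds 0.85. With X binomial(182, p), the actual one-tailed error is P(X ≥ r) at p0 and the power is P(X ≥ r) at p1.

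**Reproducing the stated 80%.** The Wald lower limit is p̂ − 1.96·√(p̂(1 − p̂)/n). For 163/182, p̂ = 0.8956 and the standard error is 0.02267, so the limit is 0.8956 − 0.0444 = 0.8512, a pass. For 162/182 it is 0.8447, a fail. So r = 163 and power is 80.7%, in line with the SAP. The actual error of this rule is 4.78%.

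**Lower limits around the boundary**

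| Agreements | Wald | Jeffreys | mid-p | Wilson | Clopper-Pearson |
|---|---|---|---|---|---|
| 163/182 | 0.8512 | 0.8450 | 0.8446 | 0.8427 | 0.8418 |
| 164/182 | 0.8577 | 0.8514 | 0.8511 | 0.8491 | 0.8482 |
| 165/182 | 0.8643 | 0.8579 | 0.8575 | 0.8555 | 0.8547 |

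**Resulting rules at n = 182**

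| Pass at | Intervals | Actual error at 85% | Power at 91.1% |
|---|---|---|---|
| ≥ 163 | Wald | 4.78% | 80.7% |
| ≥ 164 | Jeffreys, mid-p | 2.90% | 73.2% |
| ≥ 165 | Wilson, Clopper-Pearson | 1.67% | 64.4% |

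**Why this covers every interval.** At fixed n, each of these rules amounts to a cut-off on the number of agreements. Any cut-off of 163 or lower has error of at least 4.78%. Any cut-off of 164 or higher has power of at most 73.2%. No cut-off has about 80% power and at most 2.5% error.

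**Smooth approximation as a cross-check.** The score formula n = [1.96·√(p0(1 − p0)) + 0.842·√(p1(1 − p1))]² / (p1 − p0)² gives 237.6, so 238 pairs for 80% power. At 182 pairs the same approximation gives 66.6% power.

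**How often the choice decides.** At p1, P(X = 163) + P(X = 164) = 0.0748 + 0.0887 = 0.1636, or 16.4%.

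**If somewhat more than 182 pairs are analysed.** The range 182 to 195 is my illustration; the documents give no upper limit.

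| Interval | Power | Actual error |
|---|---|---|
| Wald | 76.6% to 82.7% | 3.3% to 5.0% |
| Jeffreys | 68.4% to 75.8% | 1.9% to 3.1% |
| Clopper-Pearson | 62.6% to 72.8% | 1.4% to 2.4% |

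**What Clopper-Pearson would need.** At 182 pairs, P(X ≥ 165) = 0.80 requires a true accuracy of 0.9205. At 91.1%, power first reaches 80% at 233 pairs (r = 209, power 80.8%, error 2.36%) and stays at or above 80% from 248.

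**Uncertainty of the planning value.** The Clopper-Pearson 95% interval for 133/146 is 85.3% to 95.2%.

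**The case against.** The strongest reply is that the SAP equates its 2.5% with the lower limit of a two-sided 95% interval, which is a nominal level. On that reading the Wald interval is a 2.5% rule. Its power at 182 is 80.7% exactly, or 82.3% by the normal approximation, so the stated figures coexist and there is no arithmetic slip. This probably explains the 80%. It does not rescue the claim: a rule that declares success 4.8% of the time when true accuracy is exactly 85% does not hold 2.5%. Nor does the SAP commit to Wald, and an analyst using Wilson or an exact interval would comply with every section.

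Other points stand in part:
- **Origin of 182.** The documents do not show it. Exact Wald first reaches 80% at 181, and 182 is also the smallest size with 80% power for an exact one-tailed 5% test. The cause should be left open.
- **Size of the gap.** The two-agreement gap between Wald and Clopper-Pearson holds at 182 to 184 and 189 to 192. At 185 to 188 and 193 to 195 it is one agreement. The 16.4% applies only to exactly 182 pairs.
- **Wilson instead of Clopper-Pearson.** At 182 the two give the same rule, and Wilson exceeds 2.5% only slightly (2.54% at 184, 2.55% at 192). Naming either one in advance would close the selection gap.
- **Disclosure.** Restating the power does not restore 80%. That is true, and the sponsor should see the choice plainly.

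**Conclusion.** The concern holds, and it must be fixed before the primary analysis. The deciding interval is not defined, and no interval at 182 pairs gives 80% power with an actual one-tailed error of at most 2.5%. The rule that reproduces the power has nearly twice the stated error (4.8%). The Wilson and Clopper-Pearson rules, which keep within 2.5% at 182, have 64.4% power.

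This rests on independent patients, exact binomial evaluation, exactly 182 complete pairs and a true accuracy of 133/146. Rounding the planning value hardly matters: at 0.91, Wald power is 79.4% and Clopper-Pearson power 62.6%. The conclusion that the two stated figures do not go together at 182 does not depend on how 182 was derived.

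**What to change.** 1. In SAP 2.3 and 5.2, name one interval for the primary decision: success if the lower limit of the two-sided 95% Clopper-Pearson interval for accuracy exceeds 85%, computed on the complete pairs actually analysed. With exactly 182 pairs this means at least 165 agreements. Clopper-Pearson keeps the error at or below 2.5% for every n.
2. In SAP 2.3 and Protocol 4.4, restate the power of 182 complete pairs under that rule: about 64% if true accuracy is 91.1%, and 80% if it is about 92%. The 92% is solved back from the rule and is not a planning assumption supported by the documents, so it should be labelled as such.
3. Date the change before the primary data are tabulated by device.

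The cost is wording in three sections, a less favourable stated power, and a pass mark at 182 pairs two agreements stricter than with Wald. No extra patients are needed. If the sponsor wants to keep 80% power at 91.1% under this rule, the alternative is at least 233 complete pairs, or 248 for power that stays at or above 80%. Protocol 7 schedules data collection only to November 2021 and version 4.0 is dated 25 February 2022, so that may no longer be practical.

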#### 2.4. Interim Statistical Analysis and Interrupt Rules

Not applicable.

#### 2.5. Timing of Final Analysis

All outcomes will be collectively analyzed after the last patient remains 24 hours with both systems simultaneously. The analyses will be initiated after all potential inconsistencies in the database have been resolved and the data is considered clean.

#### 2.6. Moments of Evaluation of Results

The exams performed by the conventional system (*Cardiolight*, *Cardios*) and the *QuoreOne* system will be implemented at the same time in the same patient and for the same duration. The monitoring of the electrical activity of the heart during a period of approximately 24 hours will be done by the systems, which will record the records at times according to the custom of medical practice.

The parameters will be analyzed with anonymized data from the participants.

### 3. STATISTICAL PRINCIPLES

#### 3.1. Confidence Intervals and p-Values

Two-tailed hypothesis tests with a significance level of 5% and confidence intervals of 95% will be used.

#### 3.2. Protocol Compliance and Deviations

Number (and percentage) of participants with major and minor protocol deviations will be summarized with details of the type of deviation provided. Participants included in the full set of analysis will be used as the denominator to calculate the percentages. No formal statistical testing will be performed.

#### 3.3. Analysis Populations

All individuals of both sexes, aged 18 years or older who use both systems simultaneously for 24 hours, present complete data in both examinations and have signed the consent form will be part of the Full Analysis Set (FAS).

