### 4. STUDY POPULATION

#### 4.1. Screening Data

Tables summarizing the disposition of patients will contain:

- The number of patients recruited;
- Number of patients with complete data from the two exams – % calculated from the total number of patients recruited;
- The number (%) of patients who withdrew from the study and the associated reasons (% calculated from the full set of analysis).

Unless otherwise specified, percentages will be calculated based on the number of patients in the full set of analysis.

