#### *Secondary Outcomes*

- Comparison of the detection of each type of arrhythmia between the two devices;
- Comparison of the duration of the examination between the two devices;
- Comparison of mean, minimum, and maximum heart rate captured between the two devices;
- Comparison of the total atrial ectopic heart beats captured between the two devices;
- Comparison of the total number of ventricular ectopic heart beats captured between the two devices;
- Comparison of total episodes of supraventricular tachycardia, ventricular tachycardia, and pauses between the two devices;
- Evaluate the convenience of using the two registration systems.

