### Secondary Outcomes

The individual categorical secondary endpoints (detection of each type of arrhythmia) will also be evaluated by diagnostic statistics (accuracy, sensitivity, specificity, positive and negative predictive values) with respective 95% confidence intervals.

The continuous secondary endpoints (mean, minimum and maximum heart rate, total atrial and ventricular ectopic heart beats, total episodes of supraventricular tachycardia, ventricular tachycardia and pauses) will be described by Bland-Altman plots accompanied by Lin and Pearson correlation coefficients.

Lists with the patients' reports will be made to evaluate the convenience of the systems. The Chi-square test or Fisher's exact test will be used to evaluate the proportion of patients who report greater comfort (comfort of the device) with *Quoreone* versus *Cardiolight*.

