### 5.3. Missing Data

No imputation will be performed and only analysis of complete data will be performed.

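### Complete 24-hour pairs are a fair primary set, but as the only analysis set they give withdrawals the wrong denominator, probably remove early stops from the duration endpoint, and leave exam failures unsplit by device

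*SAP*

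**What the plan says.** **Analysis set.** The FAS in SAP 3.3 consists of adults "who use both systems simultaneously for 24 hours, present complete data in both examinations and have signed the consent form". Neither document defines another set. SAP 5.3 adds: "No imputation will be performed and only analysis of complete data will be performed".

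**Disposition.** SAP 4.1 lists the number recruited, then "Number of patients with complete data from the two exams" as a percentage of those recruited, then "The number (%) of patients who withdrew from the study and the associated reasons (% calculated from the full set of analysis". The FAS is also the default denominator for the rest of that section.

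**Deviations.** SAP 3.2 promises counts and types of major and minor deviations, and states: "Participants included in the full set of analysis will be used as the denominator to calculate the percentages".

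**Duration.** The secondary outcomes in SAP 5.1 include: "Comparison of the duration of the examination between the two devices". SAP 2.6 says that the two exams "will be implemented at the same time in the same patient and for the same duration", over a period of about 24 hours. In SAP 5.2, the agreement methods cover heart rates, ectopic beats and "total episodes of supraventricular tachycardia, ventricular tachycardia and pauses) will be described by Bland-Altman plots"; duration is not in that list. SAP 5.2 also opens with a general rule that every measure from each technique is summarised with the descriptive statistics of SAP 4.5, and this covers duration.

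**The concern.** Restricting the primary analysis to complete pairs is consistent with the plan: protocol 2.1 and SAP 4.3 both set the target as 182 patients with complete data from both exams. The difficulty arises where the same set is applied to quantities that describe, or depend on, the patients it leaves out.

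- **Withdrawals.** Most withdrawals happen outside the FAS by definition, so the planned percentage is not a proportion of the patients who could withdraw.
- **Duration.** Both recordings are planned to run equally long, so a device that stops early is a main source of any difference. If those pairs are filtered out first, the two devices may look equal partly because of the filter.
- **Failures by device.** The background in SAP 1.1 argues that cable systems suffer interference that can force a repeat exam, and that a recorder worn directly on the chest gives better signals. Which device failed, and how often, bears directly on that argument. The planned tables do not ensure that it is shown.

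**Working it through.** **Plan's own figure.** The reference table in SAP 2.3 gives agreement of (83 + 50)/146 = 133/146 = 0.911. With 182 patients and the rule that the lower Wald 95% limit exceeds 85%, at least 163 agreements are needed. Exact binomial power at 0.911 is then 80.7%, which matches the stated 80%. The 182 is already a count of complete pairs, so nothing below changes it.

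**1. Withdrawal denominator.** Let d be the share of recruited patients lost before completing both exams. Assume that all of them are counted as withdrawals, and that the FAS reaches 182. The documents give no value for d, so it is varied.

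- Recruited = 182/(1 − d), rounded up; lost = recruited − 182.
- Correct percentage = lost/recruited. Planned percentage = lost/182, which is close to d/(1 − d).

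| Lost (assumed) | Recruited | % of FAS (as planned) | % of recruited |
|---|---|---|---|
| 8 | 190 | 8/182 = 4.4% | 8/190 = 4.2% |
| 21 | 203 | 21/182 = 11.5% | 21/203 = 10.3% |
| 46 | 228 | 46/182 = 25.3% | 46/228 = 20.2% |
| 78 | 260 | 78/182 = 42.9% | 78/260 = 30.0% |

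The planned figure would pass 100% once more than half were lost. Only a patient who withdrew after completing both exams could be in both numerator and denominator.

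**2. Duration.** Write D for the mean paired difference in recording time. Then

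D(all) = (1 − d) × D(complete pairs) + d × D(incomplete pairs).

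An analysis in the FAS reports only D(complete pairs). What it leaves out depends on d and on how unequal the excluded pairs are. For each hour of mean difference among the excluded pairs, the omitted term is 21/203 × 60 = 6.2 minutes with 21 lost, and 46/228 × 60 = 12.1 minutes with 46 lost. This takes all recruited patients as fitted and having a logged duration. No actual size can be given, because the documents contain no durations.

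Whether early stops really leave the FAS depends on wording. SAP 3.3 requires 24 hours of use, SAP 2.6 speaks of about 24 hours, and no tolerance is attached to complete data. Removal is therefore likely, not certain.

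**3. Failures by device.** Suppose 190 are recruited and 182 pairs are complete. SAP 4.1 prints 182/190 = 95.8% however the 8 incomplete pairs arose. If 0, 2, 4 or 8 of them were QuoreOne-only failures, the rate of such failures would be 0%, 2/190 = 1.1%, 4/190 = 2.1% or 8/190 = 4.2%. The joint rate cannot distinguish these. The number of valid observations per technique, promised through SAP 5.2 and 4.5, does not help inside the FAS, where both exams are complete by definition.

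**The case against.** The best defence is that this is a matter of reporting, and much of it is partly covered. That largely stands:

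- The withdrawal slip is small at low loss, and SAP 4.1 also reports the number recruited, so a reader can recompute the percentage.
- Duration is not left without any analysis: SAP 5.2 with 4.5 gives it a descriptive summary per device. What is absent is a method for the comparison that the endpoint promises.
- SAP 3.2 reads coherently as deviations among FAS participants. Its denominator is wrong only if deviations of patients outside the FAS are counted, and the SAP does not say that they are.
- Withdrawal reasons (SAP 4.1) and deviation types (SAP 3.2) may reveal some device failures. The accurate statement is that a split by device is not guaranteed.

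A reader might go further and infer that leaving out failed QuoreOne exams inflates the primary accuracy, perhaps enough to decide whether the 85% criterion is met. The documents do not support that. They give no failure rate, and a failed exam has no result, so whether it would have agreed is unknown; no effect at all is possible. Any count of failures said to tip the result would also depend on the interval, which the SAP does not name: 166/185 has a lower limit of 85.4% by Wald but 84.5% by Wilson. Scoring a technical failure as a diagnostic disagreement would be a different and one-sided target from the accuracy defined in SAP 5.2.

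The defence does not remove the denominator error, the mismatch between the duration endpoint and its likely analysis set, or the missing split by device.

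**Conclusion.** The point holds as a limited one. The complete-pair FAS is a legitimate primary set, but it should not be the only one.

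- **Withdrawals:** the denominator in SAP 4.1 is wrong as written. The error is about 0.2 percentage points at 8 assumed withdrawals (4.4% against 4.2%) and about 13 points at 78 (42.9% against 30.0%).
- **Duration:** the comparison is likely to be cut short by the selection rule, and no comparison method is named. The size cannot be stated from the documents.
- **Failures:** only a joint completion rate is assured.

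These conclusions rest on assumed loss counts, on an FAS of 182, and on reading SAP 3.3 literally for duration. Nothing here questions the primary analysis, the sample size or the 85% criterion.

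**What to change.** 1. **SAP 4.1:** calculate withdrawal percentages from patients recruited, as the line above it already does for complete pairs. Split incomplete pairs into QuoreOne only, Cardiolight only, both, and unknown.
2. **SAP 5.2:** compare exam duration as a paired difference with 95% CI in all consented patients fitted with both devices who have a logged duration, whether or not the recording was complete. Report how many have no logged duration.
3. **SAP 3.2:** state that the deviations table covers FAS participants, or use recruited patients as the denominator if deviations of other patients are counted.
4. Keep the complete-pair FAS for the primary analysis. No worst-case accuracy analysis is needed.

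The cost is a few lines of SAP text and a few extra tables. The main limit is data: the protocol schedule shows collection ending in November 2021, and SAP 4.2 describes patients whose simultaneous recordings were performed. Some failures may therefore never have been logged, and the unknown category and the count of missing durations make that visible.
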